10.6 Appendix 6: Collection and Management of Specimens for Future Biomedical Research

1. Definitions

- a. Biomarker: A biological molecule found in blood, other body fluids, or tissues that is a sign of a normal or abnormal process or of a condition or disease. A biomarker may be used to see how well the body responds to a treatment for a disease or condition.¹
- b. Pharmacogenomics: The investigation of variations of DNA and RNA characteristics as related to drug/vaccine response.²
- c. Pharmacogenetics: A subset of pharmacogenomics, pharmacogenetics is the influence of variations in DNA sequence on drug/vaccine response.²
- d. DNA: Deoxyribonucleic acid.
- e. RNA: Ribonucleic acid.

2. Scope of Future Biomedical Research^{3, 4}

The specimens consented and/or collected in this study as outlined in Section 8.8 will be used in various experiments to understand:

- The biology of how drugs/vaccines work
- Biomarkers responsible for how a drug/vaccine enters and is removed by the body
- Other pathways with which drugs/vaccines may interact
- The biology of disease

The specimen(s) may be used for future assay development and/or drug/vaccine development.

It is now well recognized that information obtained from studying and testing clinical specimens offers unique opportunities to enhance our understanding of how individuals respond to drugs/vaccines, enhance our understanding of human disease, and ultimately improve public health through development of novel treatments targeted to populations with the greatest need. All specimens will be used by the Sponsor or those working for or with the Sponsor.

3. Summary of Procedures for Future Biomedical Research^{3, 4}

a. Participants for Enrollment

All participants enrolled in the clinical study will be considered for enrollment in future biomedical research.

b. Informed Consent

Informed consent for specimens (ie, DNA, RNA, protein, etc) will be obtained during screening for protocol enrollment from all participants or legal guardians, at a study visit by the investigator or his or her designate. Informed consent for future biomedical research should be presented to the participants on the visit designated in the SoA. If delayed, present consent at next possible Participant Visit. Consent forms signed by the participant will be kept at the clinical study site under secure storage for regulatory reasons.

A template of each study site's approved informed consent will be stored in the Sponsor's clinical document repository.

- c. eCRF Documentation for Future Biomedical Research Specimens Documentation of participant consent for future biomedical research will be captured in the eCRFs. Any specimens for which such an informed consent cannot be verified will be destroyed.
- d. Future Biomedical Research Specimen(s) Collection of specimens for future biomedical research will be performed as outlined in the SoA. In general, if additional blood specimens are being collected for future biomedical research, these will usually be obtained at a time when the participant is having blood drawn for other study purposes.

4. Confidential Participant Information for Future Biomedical Research^{3, 4}

In order to optimize the research that can be conducted with future biomedical research specimens, it is critical to link participants' clinical information with future test results. In fact, little or no research can be conducted without connecting the clinical study data to the specimen. The clinical data allow specific analyses to be conducted. Knowing participant characteristics like sex, age, medical history, and intervention outcomes is critical to understanding clinical context of analytical results.

To maintain privacy of information collected from specimens obtained for future biomedical research, the Sponsor has developed secure policies and procedures. All specimens will be single coded per ICH E15 guidelines as described below.

At the clinical study site, unique codes will be placed on the future biomedical research specimens. This code is a random number that does not contain any personally identifying information embedded within it. The link (or key) between participant identifiers and this unique code will be held at the study site. No personal identifiers will appear on the specimen tube.

5. Biorepository Specimen Usage^{3, 4}

Specimens obtained for the Sponsor will be used for analyses using good scientific practices. Analyses using the future biomedical research specimens may be performed by the Sponsor, or an additional third party (eg, a university investigator) designated by the Sponsor. The investigator conducting the analysis will follow the Sponsor's privacy and confidentiality requirements. Any contracted third-party analyses will conform to the specific scope of analysis outlined in future biomedical research protocol and consent. Future biomedical research specimens remaining with the third party after specific analysis is performed will be reported to the Sponsor.

6. Withdrawal From Future Biomedical Research^{3, 4}

Participants may withdraw their consent for FBR and ask that their biospecimens not be used for FBR. Participants may withdraw consent at any time by contacting the study investigator. If medical records for the study are still available, the investigator will contact the Sponsor using the designated mailbox

([contact]). Subsequently, the participant's specimens

will be flagged in the biorepository and restricted to study use only. If specimens were collected from study participants specifically for FBR, these specimens will be removed from the biorepository and destroyed. Documentation will be sent to the investigator confirming withdrawal and/or destruction, if applicable. It is the responsibility of the investigator to inform the participant of completion of the withdrawal and/or destruction, if applicable. Any analyses in progress at the time of request for withdrawal/destruction or already performed before the request being received by the Sponsor will continue to be used as part of the overall research study data and results. No new analyses would be generated after the request is received.

If the medical records for the study are no longer available (eg, if the investigator is no longer required by regulatory authorities to retain the study records) or the specimens have been completely anonymized, there will no longer be a link between the participant's personal information and their specimens. In this situation, the request for withdrawal of consent and/or destruction cannot be processed.

7. Retention of Specimens^{3, 4}

Future biomedical research specimens will be stored in the biorepository for potential analysis for up to 20 years from the end of the study. Specimens may be stored for longer if a regulatory or governmental authority has active questions that are being answered. In this special circumstance, specimens will be stored until these questions have been adequately addressed.

Specimens from the study site will be shipped to a central laboratory and then shipped to the Sponsor-designated biorepository. If a central laboratory is not used in a particular study, the study site will ship directly to the Sponsor-designated biorepository. The specimens will be stored under strict supervision in a limited access facility, which operates to assure the integrity of the specimens. Specimens will be destroyed according to Sponsor policies and procedures and this destruction will be documented in the biorepository database.

8. Data Security^{3, 4}

Databases containing specimen information and test results are accessible only to the authorized Sponsor representatives and the designated study administrator research personnel and/or collaborators. Database user authentication is highly secure, and is accomplished using network security policies and practices based on international standards to protect against unauthorized access.

9. Reporting of Future Biomedical Research Data to Participants^{3, 4}

No information obtained from exploratory laboratory studies will be reported to the participant, family, or physicians. Principle reasons not to inform or return results to the participant include lack of relevance to participant health, limitations of predictive capability, and concerns regarding misinterpretation.

If important research findings are discovered, the Sponsor may publish results, present results in national meetings, and make results accessible on a public website in order to rapidly report this information to doctors and participants. Participants will not be identified by name in any published reports about this study or in any other scientific publication or presentation.

10. Future Biomedical Research Study Population^{3, 4}

Every effort will be made to recruit all participants diagnosed and treated on Sponsor clinical studies for future biomedical research.

11. Risks Versus Benefits of Future Biomedical Research^{3, 4}

10.7 Appendix 7: Country-specific Requirements

10.7.1 Germany

Section 1.3 Schedule of Activities

Study Period	Scre	ening		Т	reatm	ent Po	eriod	ЕОТ	Notes	
Week	Screening ^a (Visit 1)		1	4	8	12	16	20+ ^b	DC	
Visit Number	1		2	3	4	5	6	7+		
Scheduling	-42	-28	±3	±3	±3	±3	±3	±3	At	
Window (Days):	to -1	to –1							time	
									of DC	
Safety										
Procedures										
HIV testing	Х									Testing is required.
 a. All screening procedures should be performed within 42 days prior to treatment allocation, unless otherwise noted. b. Following Week 20, visits are to occur approximately every 4 weeks (~28 days) until documented PD, death, withdrawal of consent, or the end of the study, whichever occurs first. 										

Section 5.1 Inclusion Criteria

10. The participant provides written informed consent for the study. The participant may also provide consent for FBR. However, the participant may participate in the main study without participating in FBR.

Section 5.2 Exclusion Criteria

27. Participant has a known history of HIV infection. Testing for HIV is required at screening.

Section 8.11.1 Screening

• Laboratory tests are to be performed within 10 days prior to the first dose of study intervention randomization. An exception is HIV and hepatitis testing which may be done up to 42 days prior to the first dose of study intervention randomization.

Appendix 2 Clinical Laboratory Tests

Other Screening Tests: Serology (HIV RNA)

10.7.2 United Kingdom

Study Period	Scree	Screening Treatment Period								Notes
Week	Screening ^a (Visit 1)		1	4	8	12	16	20+ ^b	DC	
Visit Number]	1	2	3	4	5	6	7+		
Scheduling	-42	-28	±3	±3	±3	±3	±3	±3	At	
Window (Days):	to -1	to -1							time of DC	
Safety Procedures										
HIV testing	X									Testing is required.
 a. All screening procedures should be performed within 42 days prior to treatment allocation, unless otherwise noted. b. Following Week 20, visits are to occur approximately every 4 weeks (~28 days) until documented PD, death, withdrawal of consent, or the end of the study, whichever occurs first. 										

Section 5.2 Exclusion Criteria

27. Participant has a known history of human immunodeficiency virus (HIV) infection. Testing for HIV is required at screening.

Section 6.5.1 Prohibited Concomitant Medications

• Live vaccines while participating in the study, and within 90 days of the last dose of study intervention.

Examples of live vaccines include, but are not limited to, the following: measles, mumps, rubella, chickenpox, yellow fever, intranasal seasonal influenza, rabies, BCG, and typhoid (oral).

Note: Seasonal influenza vaccines for injection are generally killed virus vaccines and are allowed.

Section 8.11.1 Screening

• Laboratory tests are to be performed within 10 days prior to the first dose of study intervention randomization. An exception is HIV and hepatitis testing which may be done up to 42 days prior to the first dose of study intervention randomization.

Appendix 2 Clinical Laboratory Tests

Other Screening Tests: Serology (HIV antibody).

10.7.3 Ireland

Study Period	Scree	ening		Т	reatm	ent Pe	eriod	EOT	Notes	
Week	Screening ^a		1	4	8	12	16	20+ ^b	DC	
	(Visit I)									
Visit Number	1		2	3	4	5	6	7+		
Scheduling	-42	-28	±3	±3	±3	±3	±3	±3	At	
Window (Days):	to -1	to –1							time	
									of DC	
Safety										
Procedures			-		-	-	-			
HIV testing	Х									Testing is required.
a. All screening pro	ocedures	should be	perfor	med w	ithin 4	2 days	prior to	o treatmen	nt allocation	n, unless otherwise noted.
b. Following Week	b. Following Week 20, visits are to occur approximately every 4 weeks (~28 days) until documented PD, death,									
withdrawal of co	nsent, or	the end o	of the st	udy, w	hichev	er occu	urs first	t.		

Section 1.3 Schedule of Activities

Section 5.2 Exclusion Criteria

27. Participant has a known history of human immunodeficiency virus (HIV) infection. Testing for HIV is required at screening.

Section 6.5.1 Prohibited Concomitant Medications

• Live vaccines while participating in the study, and within 90 days of the last dose of study intervention.

Examples of live vaccines include, but are not limited to, the following: measles, mumps, rubella, chickenpox, yellow fever, intranasal seasonal influenza, rabies, BCG, and typhoid (oral).

Note: Seasonal influenza vaccines for injection are generally killed virus vaccines and, once confirmed, are allowed.

Section 8.1.4 Medical History

A medical history will be obtained by the investigator or qualified designee. The medical history will collect all active conditions and any condition diagnosed that the investigator considers to be clinically significant. Details regarding the disease for which the participant has enrolled in this study will be recorded separately and not listed as medical history.

Section 8.11.1 Screening

• Laboratory tests are to be performed within 10 days prior to the first dose of study intervention randomization. An exception is HIV and hepatitis testing which may be done up to 42 days prior to the first dose of study intervention randomization.

Appendix 2 Clinical Laboratory Tests

Other Screening Tests: Serology (HIV antibody).

10.7.4 Norway

Section 1.3 Schedule of Activities

Study Period	Screen- ing		Tre	atment P	eriod		ЕОТ		Posttre	Notes		
Visit:	Screen- ing ^a	Wk 1 Day 1 ^a	Wk 3 Day 1	Wk 5 Day 1	Wk 9 Day 1	Wk 13+ Day 1 ^b	DC	Safety Follow-up		Imaging Follow- up Visits	Survival Follow- up ^c	
Schedul-	-28 to -1	+3	±3	±3	±3	±5	At	30 Days	56 Days	Q8W	Q12W	
ing							time	After	After	or	(±7 days)	
Window							01 DC	Last Dose	Last Dose	Q12W		
Urine or serum β-hCG - WOCBP only	X	X		X	X	Q4W	X	(+/ days)	(+/ days) X*	(±/ days)		Female participants of childbearing potential will have a serum or highly sensitive urine pregnancy test within 1 day prior to randomization. If more than 1 day has elapsed between the screening pregnancy test and the first dose of study intervention, another pregnancy test (urine or serum) must be performed within 24 hours of first dose and must be negative in order for the participant to start receiving study medication. Pregnancy tests will be conducted locally.

Study	Screen-	Treatment Period					ЕОТ	Posttreatment				Notes
Period	ing											
Visit:	Screen-	Wk 1	Wk 3	Wk 5	Wk 9	Wk 13+	DC	Safety F	Safety Follow-up		Survival	
	ing ^a	Day 1 ^a	Day 1	Day 1	Day 1	Day 1 ^b					Follow-	
											up ^c	
Schedul-	-28 to -1	+3	±3	±3	±3	±5	At	30 Days	56 Days	Q8W	Q12W	
ing							time	After	After	or	(±7 days)	
Window							of	Last Dose	Last Dose	Q12W		
(Days):							DC	(+7 days)	(+7 days)	(±7 days)		

*Pregnancy testing at 56 days post EOT is only required for WOCBP on the everolimus treatment arm.

a. Week 1 Day 1 denotes the first dose of study treatment, which should be on the date of randomization, but can be within 3 days following randomization. Every effort should be made to ensure the participants receive the first dose of study intervention on the day of randomization.

b. Clinic visits after Week 13 are Q4W.

c. Long-term follow-up may be accomplished via an in-person visit, contact, medical record review, etc. Participant status information includes survival status and subsequent antineoplastic therapies for RCC.

10.7.5 Czech Republic

Section 1.3 Schedule of Activities

Study Period	Screening	ening Treatment Period EOT							Notes	
Week	Screening ^a (Visit	1	4	8	12	16	20+ ^b	DC		
	1)									
Visit Number	1	2	3	4	5	6	7+			
Scheduling Window	-28 to -1	±3	±3	±3	±3	±3	±3	At time	1	
(Days):								of DC		
Safety Procedures										
HIV testing	X								Testing is required.	
HBV testing	X								Testing is required.	
HBC testing	X								Testing is required.	
 a. All screening procedures should be performed within 28 days prior to treatment allocation, unless otherwise noted. b. Following Week 20, visits are to occur approximately every 4 weeks (~28 days) until documented PD, death, withdrawal of consent, or the end of the study, whichever occurs first. 										

Section 5.2 Exclusion Criteria

27. Has a known history of HIV infection.

Note: Testing for HIV at screening will be performed up to 28 days prior to randomization.

28. Has a known history of HBV (defined as HBsAg reactive) or known active HCV (defined as HCV RNA [qualitative] is detected) infection.

Note: Testing for HBV and HCV will be performed up to 28 days prior to randomization.

Appendix 2: Clinical Laboratory Tests

The tests detailed in Table 16 will be performed by the central laboratory.

- If local laboratory results are used to make either a study intervention decision or response evaluation, the results must be entered into the CRF.
- Protocol-specific requirements for inclusion or exclusion of participants are detailed in Section 5 of the protocol.
- Additional tests may be performed at any time during the study as determined necessary by the investigator or required by local regulations.

Confidential

140

14-NOV-2024

Laboratory Assessments	Parameters						
Hematology	Platelet Count		RBC Indices:		WBC	count with	
	KBC Count		MCH		Neutronhile		
	Hemoglobin		MCn 9/ Rationlogyt	25	Neutrophils		
	Hematocrit		76Keticulocyt	68	Lymphocytes		
					Fosipophils		
					Basan	bila	
Chemistry	PUN or urea ^b	Dotos	ium	Aspartata	Dasop	Total hilimhin	
Chemistry	BOIN OF UTea	Fotas	siuiii	Aspartate	2000	(and direct	
				$(\Lambda ST)/Sorum$	ase	(allu ullett	
				(AST)/ Serum		bilimbin is	
				Oralogoetic		alayated above the	
				Transaminasa		LIL N)	
				(SGOT)		ULN)	
	Albumin	COac	r bicarbonate	(SOOT) Chloride	Phoenhorous		
	Creatinine or CrCl ^c	Sodiu	m	Alanine		Total Protein	
	creatinine of cici	Soura	.111	Aminotransfer	ase	10tal 110telli	
				(ALT)/ Serum	n		
				Glutamic-Pyru	ivic		
				Transaminase	i v i e		
				(SGPT)			
	Glucosed	Calcin	ım	Alkaline		Triglycerides and	
	Olucose	Calen	uIII	nhosphotoso		total cholesterol	
				phosphatase		(fasting > 8 hours)	
Routine						$(1asting \ge 0 110013)$	
Urinalysis ^e	• Specific gravity						
	 pH, glucose, pro esterase] by dips 	tein, blo tick	ood, ketones, [b	oilirubin, urobilir	nogen, r	nitrite, leukocyte	
	Microscopic exa	minatio	on (if blood or p	orotein is abnorm	nal)		
Other screening	• Serum or urine	B-hCG	pregnancy test	(as needed for W	OCBP) ^e .	
Tests	• Serology (HIV,	HBsAg	and HCV anti	body) ^e .			
	Coagulation fac	tors (P]	f or INR, and a	PTT). Additiona	1 testing	to be conducted as	
	clinically indica	ted for	participants tak	ing anticoagulat	ion ther	apy.	
NOTES:	·		•				
a. Report % or	absolute results per sta	ndard o	f practice. Rep	ort the results in	the sam	e manner	
throughout th	he study.		-				
b. BUN is prefe	erred; if not available, u	irea ma	y be tested.				
c. GFR (measur	red or calculated) or Ci	Cl can	be used in plac	e of creatinine.			

 Table 16
 Protocol-required Safety Laboratory Assessments

The investigator (or medically qualified designee) must document their review of each laboratory safety report.

At baseline, the participant should be in the fasted state for glucose measurement.

To be performed locally.

d.

e.

10.7.6.3 Use of Erythropoiesis-stimulating Agents

Background and Overview

ESAs are not approved in Japan for chemotherapy-induced anemia and the Sponsor considers that ESA use for belzutifan-induced anemia is off-label use in Japan.

CCI

Study Interventions Administered

In addition to the study intervention described in Table 2, the study intervention to be used in this study specific for Japan is outlined in Table 18.

Arm	Arm	Intervention	Туре	Dose	Unit Dose	Dosage	Route of	Regimen/	Use	IMP or	Sourcing
Name	Type	Name		Formu- lation	Strength(s)	Level(s)	Adminis- tration	Treatment Period		NIMP/ AxMP	
Belzut	Experi-	M-darbe	Combination	Sterile	180 μg	360 µg	SC	Refer to	Test	IMP	Central
llan	mental		Product	Solution	syringe			for	Product		
								belzutifan-			
								induced			
								anemia			
Abbreviations: EEA = European economic area; IMP = Investigational Medicinal Product; M-darbe = darbepoetin alfa; NIMP/AxMP = Noninvestigational/Auxiliary Medicinal											
Product; $SC =$ subcutaneously.											
According to hemoglobin level, dosage levels is to be reduced as outlined in the ESA dose for belzutifan-induced anemia.											
The participants who are assigned to the belzutifan arm will be administered M-darbe according to hemoglobin level.											
M-darbe will be provided as a single-dose prefilled syringe, which is defined as a combination product (syringe device and M-darbe).											
Note: The classification of IMP and NIMP/AxMP in this table is based on guidance issued by the European Commission and applies to countries in the EEA. Country											
differences with respect to the definition/classification of IMP and NIMP/AxMP may exist. In these circumstances, local legislation is followed.											

Table 18Study Interventions

Evaluation of M-darbe for Belzutifan-induced Anemia in Japanese Participants

All Japanese participants, including the participants in the safety run-in cohort, who receive at least 1 dose of belzutifan and receive at least 1 dose of M-darbe after experiencing belzutifan-induced anemia (hemoglobin <10.0 g/dL), will be evaluated to assess the effectiveness of M-darbe in the treatment of belzutifan-induced anemia. The following endpoints will be evaluated and reported for Japanese participants:

• Percentage of participants with change from baseline in hemoglobin $\geq 2.0 \text{ g/dL}$

Percentage of participants with change from baseline in hemoglobin ≥ 2.0 g/dL will be calculated. Baseline measurement is defined as the last value measured between start date of the AE of anemia and before the first M-darbe administration for each participant. The postbaseline measurements are defined as the values measured after the start date of receiving M-darbe, and before the earliest date of 12 weeks after receiving M-darbe, the date of discontinuation of belzutifan, and the start date of blood transfusion. Change from baseline in hemoglobin will be calculated as the maximum value of postbaseline measurements minus the value of baseline measurement.

• Percentage of avoidance of a blood transfusion

Percentage of avoidance of a blood transfusion will be calculated and is defined as the percentage of participants who did not receive a blood transfusion.

- The percentage of participants whose minimum value of post-baseline measurements of hemoglobin ≥7.0 g/dL
- The percentage of participants whose minimum value of post-baseline measurements of hemoglobin ≥8.0 g/dL

In addition, AEs will also be summarized for all participants included in this evaluation of M-darbe.

AE Monitoring and Reporting Related to M-darbe

Based on Sections 1.3 and 8.4, AE monitoring of administration of M-darbe, which is considered as an IMP in Japan, will also be performed. Treatment with M-darbe is considered as study intervention, and therefore, the time period for collecting AE, SAE, and other reportable safety event information will be as described in Section 8.4.1.

Concomitant Therapy

Based on Section 6.5, all concomitant medications received within 28 days before randomization and up to 30 days after the last dose of study intervention, defined by the last dose of belzutifan, everolimus, or M-darbe should be recorded. Concomitant medications administered >30 days after the last dose of study intervention defined by the last dose of belzutifan, everolimus, or M-darbe should be recorded for SAEs as defined in Section 8.4.

Serious Syringe Device Events (Incidents)

M-darbe will be provided as a single-dose prefilled syringe, which is defined as a combination product (syringe device and M-darbe). A syringe device corresponds to a medical device, and serious syringe device events (incidents) must be reported to the Sponsor.

Instructions for medical device use are provided in the Pharmacy Manual.

Definition of Serious Syringe Device Events (Incidents)

A serious syringe device event (incident) is any malfunction or deterioration in the characteristics and/or performance of the device, as well as any inadequacy in the labeling or the instructions for use that, directly or indirectly, led to the death of a participant or user, or of other persons, or to a serious deterioration in their state of health.

A serious deterioration in the state of health can include:

- 1. Life-threatening illness;
- 2. Permanent impairment of a body function or permanent damage to a body structure;
- 3. A condition necessitating medical or surgical intervention to prevent 1 or 2;
- 4. A condition that requires hospitalization or significant prolongation of existing hospitalization; or
- 5. Fetal distress, fetal death, or any congenital abnormalities or birth defects.

Definition of Malfunction Which may Lead to Serious Adverse Events - Any malfunction of a medical device which might have led to the death of a participant and/or the associated person or to a serious deterioration in his/her state of health. "Which might have led to" means that there is the possibility that death or a serious deterioration might have occurred in a participant and/or the associated person, although these cases have not actually occurred.

Monitoring, Reporting, and Follow-up of Serious Syringe Device Events (Incidents)

For the time period beginning when the consent form is signed through the duration of the participant's study participation, any serious syringe device event (incident), including follow-up to an incident and death due to any cause, that occurs to any participant must be reported within 24 hours to the Sponsor both by paper reporting for the event (incident) and electronic reporting for SAEs. Malfunction which may lead to SAEs will be reported to the Sponsor within 5 calendar days of learning of the information via a paper reporting form.

Any serious syringe device event (incident) that occurs in study personnel must be reported within 24 hours to the Sponsor both by paper reporting for the event (incident) and spontaneous reporting to the Sponsor.

Paper reporting procedures can be found in the Investigator Trial File Binder (or equivalent).

Additionally, any serious syringe device event (incident) considered by an investigator who is a qualified physician to be related to the Sponsor's product that is brought to the attention of the investigator at any time outside of the time period specified above must be reported immediately to the Sponsor.

All participants involved with serious syringe device events (incidents) must be followed up for outcome.

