10.8.3 Anemia Management

Decreased EPO is the potential etiology of anemia with belzutifan treatment. EPO replacement is an effective management strategy for participants who may develop and subsequently require intervention for belzutifan-induced anemia. Transfusion can also be used to manage anemia in patients receiving belzutifan.

155

Grade 3 events (report as ECI):

• Dose Modification not required

Grade 4 events (report as ECI):

- First episode: Hold belzutifan. Once toxicity has resolved to ≤Grade 2 or baseline, dose reduce belzutifan by 1 level
- Second episode: Permanently discontinue belzutifan

All attempts should be made to rule out other causes of anemia. Relevant diagnostic studies may include peripheral blood smear, reticulocyte count, LDH, haptoglobin, Coomb's test, blood levels of vitamin B12, folate, iron studies, etc.

While dose interruption is not required, the investigator may elect to hold belzutifan for participants who develop anemia Grade 1-3. If belzutifan is held for anemia Grade 1-3, the participant can be re-challenged with belzutifan at the same dose.

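### The Japan M-darbe hemoglobin response can count recovery during a belzutifan hold or after a dose reduction, because neither ends its window; transfusion avoidance has no stated window

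*Protocol*

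**What the plan says.** Protocol 10.7.6.3 covers Japanese participants, including the safety run-in cohort, who took belzutifan and received at least one M-darbe dose after belzutifan-induced anemia with hemoglobin below 10.0 g/dL. They "will be evaluated to assess the effectiveness of M-darbe in the treatment of belzutifan-induced anemia".

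- **Measure.** "Change from baseline in hemoglobin will be calculated as the maximum value of postbaseline measurements minus the value of baseline measurement". The success threshold is a rise of 2.0 g/dL or more.
- **Window.** Values count after M-darbe starts and "before the earliest date of 12 weeks after receiving M-darbe, the date of discontinuation of belzutifan, and the start date of blood transfusion".
- **Transfusion avoidance.** This is "defined as the percentage of participants who did not receive a blood transfusion". No period is given.

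The dosing rules stand elsewhere. Protocol 10.8.3 says that "While dose interruption is not required, the investigator may elect to hold belzutifan for participants who develop anemia Grade 1-3", with re-challenge at the same dose. For the first Grade 4 episode, Table 3 and 10.8.3 call for a hold and then a one-level reduction. SAP 3.6.5 plans listings and an adverse-event table for the run-in cohort and does not mention the M-darbe endpoints.

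**The concern.** The window closes at belzutifan discontinuation and at transfusion. Both are events after which hemoglobin may rise for reasons other than M-darbe. The protocol does not give that as its reason, but it is the natural one, and a hold or a dose reduction raises the same difficulty: the suspected cause of the anemia is removed or lessened while values continue to count. Because the maximum is scored, one qualifying value is enough.

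At stake is the reading of an effectiveness percentage for a product that the protocol classes as an IMP in Japan and whose use for this anemia it describes as off-label there. With no comparator described, the percentage cannot separate the effect of M-darbe from recovery after less belzutifan.

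**Working it through.** The plan states no sample size, target rate or hold rate for this endpoint, so there is no figure to reproduce. The check is mainly textual.

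**1. Is a hold already covered by discontinuation?** Protocol 6.6.1 allows interruption for adverse events at the investigator's discretion and asks for Sponsor consultation beyond 28 days. Section 7.1 makes an interruption a ground for discontinuation only when it exceeds 28 consecutive days without that consultation. Section 10.8.3 describes holds with re-challenge. Interruption and discontinuation are therefore separate terms. Even if discontinuation were read to include temporary stopping, dose reduction would remain uncovered.

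**2. Can a hold fall in this population?** Entry at hemoglobin below 10.0 g/dL corresponds to Grade 2 or worse (10.8.2). Holds are optional through Grade 3 and required at the first Grade 4 episode. Table 3 adds holds for other toxicities.

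**3. How much of the window can a hold occupy?** Reading the 12 weeks as running from the first M-darbe dose:

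- Window: 12 × 7 = 84 days.
- Hold needing no Sponsor consultation: up to 28 days, and 28 / 84 = one third of the window.
- Average rise needed for success: 2.0 / 12 = 0.17 g/dL per week over the whole window, or 2.0 / 4 = 0.5 g/dL per week if it all fell within a 28-day hold.
- Drug clearance: Protocol 2.2.6 gives a mean steady-state half-life of 15.4 hours at 120 mg QD. Five half-lives are 5 × 15.4 = 77 hours, about 3.2 days, so most of a hold of several weeks is spent with little drug present. The documents do not say how fast hemoglobin follows.

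**4. Direction for the 2.0 g/dL endpoint.** Adding values can only raise a maximum or leave it unchanged. Keeping values from after a hold or reduction can therefore add responders and cannot remove any.

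**5. Size, by illustration only.** Let p be the share who would respond to M-darbe alone, h the share with a hold or reduction in the window, and r the share of those whose rise reaches 2.0 g/dL only because of it. With independence assumed, the added response is h × r × (1 − p). None of these inputs is in the documents. The assumed ranges are p 20-60%, h 10-50% and r 10-50%.

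| p | h | r | Added response |
|---|---|---|---|
| 60% | 10% | 10% | 0.10 × 0.10 × 0.40 = 0.4 points |
| 40% | 30% | 25% | 0.30 × 0.25 × 0.60 = 4.5 points (40% becomes 44.5%) |
| 20% | 50% | 50% | 0.50 × 0.50 × 0.80 = 20 points |

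The spread shows only that the answer depends on the assumptions.

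**6. Transfusion avoidance.** With no window, a participant who stops belzutifan soon after one M-darbe dose and is never transfused counts as a success. A participant transfused long after M-darbe, or after belzutifan has stopped, counts as a failure. The two effects oppose each other, so no net direction follows.

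**The case against.** The strongest reply is that holds and reductions are part of protocol management, so counting hemoglobin through them is a defensible treatment-policy choice. Ending the window at every hold would also drop genuine M-darbe responses after holds for unrelated toxicities. This stands, and it is why the truncated analysis should accompany the current definition and not replace it.

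Other parts of the reply also stand:

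- A reader might infer that holds are common among M-darbe recipients. The documents give no rate. Section 10.8.3 requires no dose modification at Grade 3 and calls EPO replacement effective.
- The transfusion stop already removes some of the severest cases, though not every held participant is transfused.
- From Week 13, scheduled hematology is every 4 weeks, so a hold shorter than that may contain only about one scheduled value. Under a maximum rule, one value can suffice.
- Held participants may be those responding poorly to M-darbe, so a simple comparison of held with non-held participants would not measure the inflation.
- Parts of 10.7.6 are redacted, apparently including the ESA dosing rules. A Japan-specific provision on holds may exist there. The visible endpoint definition lists only three end dates.

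A reader might also propose Kaplan-Meier transfusion avoidance with censoring at a hold. That censoring would be informative: a hold for worsening anemia selects participants closer to transfusion, so the avoidance estimate could itself be inflated.

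**Conclusion.** The gap is real and of low severity. As visibly defined, the 2.0 g/dL response can credit M-darbe with recovery that occurred during a belzutifan hold or after a reduction, and no visible text in the protocol or SAP corrects for it. The direction follows from the use of the maximum. The size does not follow from the documents, and the illustrative 0.4 to 20 points should not be quoted as an estimate.

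Two stronger readings are not supported. The documents do not show that the reported rate will be materially inflated, since that needs hold and recovery rates they do not give. Nor do they show that transfusion avoidance is biased in favour of M-darbe; they show only that it is not aligned with the hemoglobin endpoint. The evaluation is descriptive, with no stated hypothesis test, and PFS, OS, ORR and the alpha allocation are unaffected.

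The conclusion rests on discontinuation meaning permanent stopping, as the rest of the protocol uses it, and on the redacted text containing no rule that already handles holds.

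**What to change.** Change the analysis text only; no dosing or management rule is touched.

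1. Keep the current 2.0 g/dL definition. Beside it, report the response with post-baseline values ending also at the first belzutifan hold or dose reduction. State how participants already on hold at the first M-darbe dose are counted.
2. Give the number of responders whose qualifying value fell during or after a hold or reduction.
3. Report transfusion avoidance over the 12 weeks from the first M-darbe dose. Show participants with a hold, reduction or discontinuation separately and do not censor them.

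The truncation is not proposed for the two minimum-hemoglobin percentages (7.0 and 8.0 g/dL), where dropping later values could only raise the result.

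The cost is a few sentences in the Japan appendix or the SAP. Transfusions are already recorded as concomitant therapy (Protocol 6.5), and dose interruptions due to adverse events are already summarised (SAP Table 4). The truncated analysis has fewer evaluable values per participant and loses some genuine M-darbe responses that follow unrelated holds.
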